**d. Results in persistent disability/incapacity**

The term *disability* means a substantial disruption of a person’s ability to conduct normal life functions.

This definition is not intended to include experiences of relatively minor medical significance such as uncomplicated headache, nausea, vomiting, diarrhea, influenza, and accidental trauma (eg, sprained ankle) which may interfere with or prevent everyday life functions but do not constitute a substantial disruption.

**e. Is a congenital anomaly/birth defect**

**f. Other situations:**

Medical or scientific judgment should be exercised in deciding whether SAE reporting is appropriate in other situations such as important medical events that may not be immediately life threatening or result in death or hospitalization but may jeopardize the participant or may require medical or surgical intervention to prevent one of the other outcomes listed in the above definition. These events should usually be considered serious.

Examples of such events include invasive or malignant cancers, intensive intervention in an emergency room or at home for allergic bronchospasm, blood dyscrasias or convulsions that do not result in hospitalization, or development of drug dependency or drug abuse.

Allergan considers all cancer AEs as SAEs. In addition, Allergan considers any abortion (spontaneous or elective) as an SAE.

Preplanned surgeries or procedures for pre-existing, known medical conditions for which a participant requires hospitalization are not reportable as an SAE.

Any preplanned surgery or procedure should be clearly documented in the site source documents by the medically qualified investigator at the time of the participant's entry into the study. If it has not been documented at the time of the participant's entry into the study, then it should be documented as a SAE and reported to Allergan.

### 9.1.3 Intensity

The intensity assessment for a clinical AE must be completed using the following definitions as guidelines:

Assessment of Intensity	
MILD	A type of AE that is usually transient and may require only minimal treatment or therapeutic intervention. The event does not generally interfere with usual activities of daily living.
MODERATE	A type of AE that is usually alleviated with additional specific therapeutic intervention. The event interferes with usual activities of daily living, causing discomfort but poses no significant or permanent risk of harm to the research participant.
SEVERE	A type of AE that interrupts usual activities of daily living, or significantly affects clinical status, or may require intensive therapeutic intervention.

An event is defined as *serious* when it meets at least one of the predefined outcomes as described in the definition of an SAE, NOT when it is rated as severe.

### 9.1.4 Assessment of Causality

#### Assessment of Causality

- The investigator is obligated to assess the relationship between atogepant and each occurrence of each AE or SAE.
- A *reasonable possibility* of a relationship conveys that there are facts, evidence, and/or arguments to suggest a causal relationship, rather than a relationship cannot be ruled out.
- The investigator will use clinical judgment to determine the relationship.
- Alternative causes, such as underlying disease(s), concomitant therapy, and other risk factors, as well as the temporal relationship of the event to atogepant administration will be considered and investigated.
- The investigator will also consult the investigator's brochure in his/her assessment.
- For each AE or SAE, the investigator **must** document in the medical notes that he/she has reviewed the AE or SAE and has provided an assessment of causality.
- There may be situations in which an SAE has occurred, and the investigator has minimal information to include in the initial report to Allergan. However, **it is very important that the investigator always make an assessment of causality for every event before the initial transmission of the SAE data to Allergan.**
- The investigator may change his/her opinion of causality in light of follow-up information and send an SAE follow-up report with the updated causality assessment.
- The causality assessment is one of the criteria used when determining regulatory reporting requirements.

### 9.1.5 Follow-up of Adverse Events and Serious Adverse Events

After the initial AE/SAE report, the investigator is required to proactively follow each participant at subsequent visits/contacts. All AEs/SAEs and non-serious AEs of special interest (as defined in [Section 6.5.2](#)) will be followed until resolution, stabilization, the event is otherwise explained, or the participant is lost to follow-up (as defined in [Section 8.8](#)).

The investigator is obligated to perform or arrange for the conduct of supplemental measurements and/or evaluations as medically indicated or as requested by Allergan to elucidate the nature and/or causality of the AE or SAE as fully as possible. This may include additional laboratory tests or investigations, histopathological examinations, or consultation with other health care professionals.

Prior to database lock, new or updated information will be recorded in the originally completed eCRF. If the event is an SAE, it will also need to be reported on the SAE reporting form. Post

database lock, new or updated SAE information will only be reported on the SAE reporting form.

The investigator will submit any updated SAE data to Allergan within 24 hours of receipt of the information.

## **9.2 Procedures for Reporting Adverse Events**

All AEs must be recorded on the appropriate eCRF.

All AEs that are atogepant-related and unexpected (not listed as treatment-related in the current investigator's brochure) must be reported to the governing IRB/IEC as required by the IRB/IEC, local regulations, and the governing health authorities. Any AE that is marked 'ongoing' at the exit visit must be followed-up as appropriate.

## **9.3 Procedures for Reporting a Serious Adverse Event**

Any SAE occurring during the study period (beginning with informed consent) until the EOS Visit (Visit 12) or 30 days after the last dose of atogepant if the EOS Visit is not done must be immediately reported but no later than 24 hours after learning of an SAE. SAEs must be reported to Allergan as listed on the Allergan Study Contacts Page and recorded on the SAE form. All participants with an SAE must be followed up and the outcomes reported. The investigator must supply Allergan and the IRB/IEC with any additional requested information (eg, autopsy reports and discharge summaries).

### **9.3.1 Regulatory Reporting Requirements for Serious Adverse Events**

- Prompt notification by the investigator to Allergan of an SAE is essential so that legal obligations and ethical responsibilities towards the safety of participants and the safety of a study intervention (ie, atogepant) under clinical investigation are met.
- Allergan has a legal responsibility to notify both the local regulatory authority and other regulatory agencies about the safety of a study intervention (ie, atogepant) under clinical investigation. Allergan will comply with country-specific regulatory requirements relating to safety reporting to the regulatory authority, IRBs/ IECs, and investigators.
- Investigator safety reports must be prepared for SUSARs according to local regulatory requirements and Allergan policy and forwarded to investigators as necessary.

- An investigator who receives an investigator safety report describing an SAE or other specific safety information (eg, summary or listing of SAEs from Allergan) will review and then file it along with the investigator's brochure and will notify the IRB/IEC, if appropriate according to local requirements.

## 9.4 Exposure to Study Intervention During Pregnancy

Details of all pregnancies in female participants and female partners of male participants will be collected after the start of atogepant and until the EOS Visit (Visit 12) or 30 days after the last dose of atogepant if the EOS Visit is not done. Study center personnel must report every pregnancy on the Pregnancy Form (within 24 hours of learning of the pregnancy to the Serious Adverse Event Reporting Fax Number[s]: [contact] [back up [contact]], email: [contact]), even if no AE has occurred. The pregnancy must be followed to term and the outcome reported by completing a follow-up Pregnancy Form. Abnormal pregnancy outcomes (eg, spontaneous or elective abortion, fetal death, stillbirth, congenital anomalies, ectopic pregnancy) are considered SAEs. For pregnancy related SAEs, in addition to the Pregnancy Form, a separate SAE Form must be filed as described in [Section 9.3](#) with the appropriate serious criterion (eg, hospitalization) indicated.

## 9.5 ALT or AST Elevations

A treatment-emergent ALT  $\geq 3 \times$  ULN and/or AST  $\geq 3 \times$  ULN is considered an AESI. Any participant with this laboratory result after atogepant was taken must have repeat testing within 48 to 72 hours to confirm the abnormality. For this repeat testing, the following laboratory tests must be performed: hematology and chemistry panels, INR, serum acetaminophen level, urine drugs of abuse screen, and blood alcohol level. An extra blood serology sample must be collected and sent to the central laboratory for further diagnostic testing, at a later date, if needed. In addition, the investigator will perform a complete history and examination to evaluate the participant for possible liver disease.

All AEs of special interest must be reported to Allergan within 24 hours of the time the investigator becomes aware of the event using the abnormal liver function reporting form and the AE eCRF. All new elements of history, physical examination, diagnostic testing results, and other relevant medical reports are to be reported for each AE of special interest.

**If an ALT or AST  $\geq 3 \times$  ULN is confirmed, close medical follow-up is required:**

For these participants, the following laboratory tests must be performed: anti-hepatitis A IgM, hepatitis B surface antigen, anti-hepatitis B core IgM, hepatitis C antibody, hepatitis C

quantitative RNA by polymerase chain reaction, anti-hepatitis E IgM, anti-hepatitis E IgG, Cytomegalovirus IgM antibody and Epstein-Barr Virus IgM antibody. The participant must be followed clinically and further medical evaluation (for other causes of acute hepatic injury) should be done per the judgment of the investigator and in conjunction with medical personnel at Allergan. In general, the chemistry panel should be repeated 1 to 2 times per week to follow the course of ALT/AST elevation.

**Atogepant must be discontinued if any of the following criteria are met:**

- ALT or AST  $\geq 3 \times$  ULN and the participant is symptomatic with the appearance of fatigue, nausea, vomiting, right upper quadrant pain or tenderness, fever, rash, or eosinophilia ( $> 5\%$ )
- ALT or AST  $\geq 3 \times$  ULN and total bilirubin  $> 2 \times$  ULN
- ALT or AST  $\geq 3 \times$  ULN and INR  $> 1.5$
- ALT or AST  $\geq 5 \times$  ULN for more than 2 weeks
- ALT or AST  $\geq 8 \times$  ULN

The participant may be rechallenged with atogepant only after consultation with the Allergan Medical Monitor. For participants who are not rechallenged, the participant should be discontinued from the study and complete an ET Visit and an EOS Visit 4 weeks later. Participants should receive appropriate follow-up as per standard of care.

**The investigator must contact the Allergan Medical Monitor to discuss all cases of confirmed ALT/AST elevation  $\geq 3 \times$  ULN. All ALT/AST elevations must be followed until ALT and AST return to  $< 1.5 \times$  ULN and there is full clinical resolution.**

### **9.5.1 Potential Hy's Law Cases**

Sites must report every participant who meets the following potential Hy's law criteria if this occurs within the time the participant signs the ICF until 30 days after the last dose of atogepant:

- ALT or AST  $\geq 3 \times$  ULN **AND**
- Total bilirubin  $\geq 2 \times$  ULN **AND**
- Alkaline phosphatase  $< 2 \times$  ULN

Study site personnel must report every participant who meets these criteria. Typically, all 3 analytes will be obtained from the same sample, but they may come from multiple samples taken within a 24-hour period. This requirement applies from the time the participant signs the

ICF for the study until 30 days after the final protocol-defined study visit or the last known dose of atogepant (if the final visit does not occur).

A laboratory alert for possible Hy's law cases will be in place and must notify investigators and Allergan immediately when the above criteria have been met. A possible Hy's law case must be faxed to Allergan on an abnormal liver function reporting form as soon as possible (within 24 hours of learning of the possible Hy's law case) to the fax number on the form or the SAE fax number, even if no AE has occurred. If the event is serious, please complete the AESI/SAE form. The eCRF for possible Hy's law cases must be completed within 7 calendar days. Every effort to determine the cause of the liver enzyme abnormalities must be made, and close monitoring should be initiated in conjunction with the medical monitor and medical safety physician and in accordance with the FDA Guidance for Industry, Drug-Induced Liver Injury: Premarketing Clinical Evaluation, July 2009. The participant should return to the study site and be evaluated as soon as possible, preferably within 48 hours from the time the investigator becomes aware of the abnormal results. This evaluation should include laboratory tests, detailed history, and physical assessment.

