Potential Hy's Law criteria within a 24-hour window is defined by a postbaseline elevation of alanine aminotransferase (ALT) or aspartate aminotransferase (AST) $\geq 3 \times$ ULN, along with total bilirubin (TBL) $\geq 2 \times$ ULN and a non-elevated alkaline phosphatase (ALP) $< 2 \times$ ULN, all based on blood draws collected within a 24-hour period. Participants who meet the potential Hy's Law criteria from the first dose of study treatment to the end of study will be summarized. Supportive tabular displays will also be provided.

Table 11-1 Criteria for Potentially Clinically Significant Laboratory Values

Category	Parameter	SI Unit	PCS Criteria	
			PCS Low	PCS High
Chemistry	Albumin	g/L	< 0.8 × LLN	> 1.2 × ULN
	Alanine aminotransferase	U/L	—	≥ 3.0 × ULN
	Alkaline phosphatase	U/L	—	≥ 3.0 × ULN
	Aspartate aminotransferase	U/L	—	≥ 3.0 × ULN
	Bicarbonate	mmol/L	< 0.9 × LLN	> 1.1 × ULN
	Bilirubin, total	μmol/L	—	≥ 1.5 × ULN
	Blood urea nitrogen	mmol/L	—	> 1.5 × ULN
	Calcium	mmol/L	< 0.9 × LLN	> 1.1 × ULN
	Chloride	mmol/L	< 0.9 × LLN	> 1.1 × ULN
	Cholesterol, total	mmol/L	—	> 1.6 × ULN
	Creatinine	μmol/L	—	> 1.5 × ULN
	Creatine kinase	U/L	—	> 2.0 × ULN
	Estimated glomerular filtration rate	mL/min/1.73m ²	<60 mL/min/1.73 m ²	—
	Glucose, nonfasting	mmol/L	< 0.8 × LLN	> 2.0 × ULN
	Lactate dehydrogenase (LDH)	U/L	—	> 3.0 × ULN
	Phosphorus	mmol/L	< 0.9 × LLN	> 1.1 × ULN
	Potassium	mmol/L	< 0.9 × LLN	> 1.1 × ULN
	Protein, total	g/L	< 0.9 × LLN	> 1.1 × ULN
	Sodium	mmol/L	< 0.9 × LLN	> 1.1 × ULN
	Uric acid	μmol/L	—	> 1.2 × ULN
Hematology	Basophils, absolute cell count	10 ⁹ /L	—	> 2.0 × ULN
	Eosinophils, absolute cell count	10 ⁹ /L	—	> 2.0 × ULN
	Hematocrit	Ratio	< 0.9 × LLN	> 1.1 × ULN
	Hemoglobin	g/L	< 0.9 × LLN	> 1.1 × ULN
	Lymphocytes, absolute cell count	10 ⁹ /L	< 0.7 × LLN	> 1.3 × ULN
	Monocytes, absolute cell count	10 ⁹ /L	< 0.5 × LLN	> 2.0 × ULN
	Neutrophils, absolute cell count	10 ⁹ /L	< 0.7 × LLN	> 1.3 × ULN
	Platelet count	10 ⁹ /L	< 0.5 × LLN	> 1.5 × ULN
	Red blood cell count	10 ¹² /L	< 0.9 × LLN	> 1.1 × ULN
	White blood cell count	10 ⁹ /L	< 0.9 × LLN	> 1.5 × ULN
Urinalysis	pH	pH	< 0.9 × LLN	> 1.1 × ULN
	Glucose		—	At least 1+
	Protein		—	At least 1+
	Specific gravity	—	—	> 1.1 × ULN

LLN = lower limit of normal value; ULN = upper limit of normal value; normal value provided by laboratory.

SI = Le Système International d'Unités (International System of Units).

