The number and percentage of participants meeting each of the following criteria for postbaseline hepatic laboratory abnormalities listed in Table 11-2 will be summarized. The percentages will be calculated relative to the number of participants with at least 1 available postbaseline assessment. The numerator will be the total number of participants having at least 1 postbaseline value that meets the specific category during the study. A supportive listing will also be provided.

Table 11-2 Criteria for Hepatic Laboratory Abnormalities

Laboratory Parameter	Categories
ALT	$\geq 1 \times \text{ULN}$
	$\geq 1.5 \times \text{ULN}$
	$\geq 2 \times \text{ULN}$
	$\geq 3 \times \text{ULN}$
	$\geq 5 \times \text{ULN}$
	$\geq 10 \times \text{ULN}$
	$\geq 20 \times \text{ULN}$
AST	$\geq 1 \times \text{ULN}$
	$\geq 1.5 \times \text{ULN}$
	$\geq 2 \times \text{ULN}$
	$\geq 3 \times \text{ULN}$
	$\geq 5 \times \text{ULN}$
	$\geq 10 \times \text{ULN}$
	$\geq 20 \times \text{ULN}$
ALT or AST	$\geq 1 \times \text{ULN}$
	$\geq 1.5 \times \text{ULN}$
	$\geq 2 \times \text{ULN}$
	$\geq 3 \times \text{ULN}$
	$\geq 5 \times \text{ULN}$
	$\geq 10 \times \text{ULN}$
	$\geq 20 \times \text{ULN}$
Bilirubin Total	$\geq 1 \times \text{ULN}$
	$\geq 1.5 \times \text{ULN}$
	$\geq 2 \times \text{ULN}$
	$\geq 3 \times \text{ULN}$
	$\geq 5 \times \text{ULN}$
	$\geq 10 \times \text{ULN}$
	$\geq 20 \times \text{ULN}$
Alkaline Phosphatase	$\geq 1 \times \text{ULN}$
	$\geq 1.5 \times \text{ULN}$
	$\geq 2 \times \text{ULN}$
	$\geq 3 \times \text{ULN}$
	$\geq 5 \times \text{ULN}$
	$\geq 10 \times \text{ULN}$
	$\geq 20 \times \text{ULN}$

Laboratory Parameter	Categories
Concurrent Elevations ¹	ALT or AST $\geq 3 \times$ ULN and Bilirubin Total $\geq 1.5 \times$ ULN ALT or AST $\geq 3 \times$ ULN and Bilirubin Total $\geq 2 \times$ ULN
Potential Hy's Law within 24-hour window ¹	Postbaseline assessment of the following laboratory parameters based on blood draws collected within a 24-hour period: 
• ALT or AST $\geq 3 \times$ ULN• TBL $\geq 2 \times$ ULN• ALP $< 2 \times$ ULN
e-DISH	Postbaseline assessment of the following laboratory parameters at any time: 
• Maximum ALT or AST $\geq 3 \times$ ULN• Maximum TBL $\geq 2 \times$ ULN

ALT = alanine aminotransferase; AST = aspartate aminotransferase; TBL = total bilirubin;
ALP = alkaline phosphatase; ULN = upper limit of normal (value provided by the laboratory).

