¹ Elevations are from the same day

The number and percentage of participants with an adjudicated case (i.e., ALT $\geq 3 \times$ ULN and/or AST $\geq 3 \times$ ULN) will be summarized and by relationship of ALT or AST elevation to study medication. The percentages will be calculated relative to the number of participants with at least 1 adjudicated case. The numerator will be the number of participants with at least 1 adjudicated case in the specific category of relationship. If a participant has more than 1 adjudicated case, he or she will be counted in the most relevant category of relationship.

Participants with an adjudicated case (i.e. ALT $\geq 3 \times$ ULN or AST $\geq 3 \times$ ULN) will be listed with their ALT and AST assessments, adjudication dates, relationship of ALT or AST elevation to study medication, and confounding factor(s). Additional listings will be provided for participants who meet ALT $\geq 3 \times$ ULN or AST $\geq 3 \times$ ULN and/or potential Hy's law and have one of the following categories: at least 1 abnormal liver biochemistry risk factor, at least 1 liver disease sign and symptom, at least 1 liver diagnostic test performed, consultation with a specialist for liver evaluation, liver lab tests performed, and drug screen performed, respectively.

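### Potential Hy's law cases have two reporting end dates in Protocol 9.5.1, an undefined counting window in SAP 11.2, and a same-day footnote that contradicts the 24-hour rule

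*Protocol*

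**What the plan says.** **Reporting period.** Protocol Section 9.5.1 opens by requiring sites to report a participant who meets the criteria "if this occurs within the time the participant signs the ICF until 30 days after the last dose of atogepant". After the criteria, the same section restates the requirement as running from consent "until 30 days after the final protocol-defined study visit or the last known dose of atogepant", with the dose as the anchor only if the final visit is not held.

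**Counting period.** SAP Section 11.2 summarizes participants who meet the criteria "from the first dose of study treatment to the end of study". No day number is given there. Section 18.1 gives End of Study two meanings. The row in Table 18.1-1 places it at the final visit, expected on Day 280, or at early termination. The note under the table makes it the last assessment on record with the safety follow-up period included.

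**Concurrency.** Protocol 9.5.1 accepts analytes from several samples taken within 24 hours. The SAP text and the potential Hy's law row of Table 11-2 agree: the row is "based on blood draws collected within a 24-hour period". The row label also carries footnote 1, which reads "Elevations are from the same day". The Concurrent Elevations row carries the same footnote.

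**Testing after the last visit.** Protocol Section 9.5 says "All ALT/AST elevations must be followed until ALT and AST return to" below 1.5 × ULN with full clinical resolution. For confirmed elevations it adds that the chemistry panel is, in general, repeated once or twice a week.

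**The concern.** Safety is the only objective of this study, and potential Hy's law is a named adverse event of special interest in Protocol Section 6.5.2. Table 11-2 has a single row that counts it. With such rare events the count may be zero or one, so a rule that leaves one case in or out changes what the table says.

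There are two separate weaknesses. First, a site reading Section 9.5.1 cannot tell when its duty ends, and a programmer reading the SAP cannot tell when counting ends. Follow-up liver tests may continue past Visit 12 in a participant whose elevation has not resolved, and it is in such a participant that bilirubin might later rise. Second, a programmer who applies footnote 1 literally will exclude a case that the row itself, the SAP text and the protocol all include.

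**Working it through.** No sample size, power or error rate is involved. The check is date arithmetic on the documents' own schedule and a comparison of two concurrency rules.

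**1. Anchors.** Week 40 is 40 × 7 = Day 280 and Week 44 is 44 × 7 = Day 308. The end-of-study visit is 4 weeks after the last dose: 280 + 28 = 308. The schedule is consistent with itself.

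**2. The two ends in Protocol 9.5.1.** First sentence: last dose + 30. Second sentence: final visit + 30, or last dose + 30 if that visit does not occur.

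| Participant | Last dose | Visit 12 | First sentence | Second sentence | Difference |
|---|---|---|---|---|---|
| Completer, on schedule | 280 | 308 | 280 + 30 = 310 | 308 + 30 = 338 | 28 days |
| Early stop (example) | 100 | 128 | 100 + 30 = 130 | 128 + 30 = 158 | 28 days |
| Completer, no Visit 12 | 280 | none | 310 | 310 | 0 |

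If the last dose and Visit 12 may each move by 3 days, the difference runs from 335 − 313 = 22 days (last dose Day 283, Visit 12 Day 305) to 341 − 307 = 34 days (last dose Day 277, Visit 12 Day 311).

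**3. The SAP end.** For the on-schedule completer, the Table 18.1-1 row gives Day 280. The note under the table gives Day 308 if Visit 12 is the last assessment, and a later day if an unscheduled follow-up test counts as an assessment during the study. Section 18.3 uses the last non-missing postbaseline value as the end-of-study assessment when unscheduled visits occur, which leans towards the later reading but does not settle it. If Day 308 is taken, it lies 310 − 308 = 2 days before the first protocol end and 338 − 308 = 30 days before the second.

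**4. A case between the dates.** Suppose the criteria are first met on Day 320. The case is outside the first sentence of 9.5.1 and inside the second. It may or may not be inside the SAP count, depending on the meaning of End of Study.

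**5. Same day against 24 hours.** Take ALT at 16:00 and bilirubin at 09:00 the next morning. They are 17 hours apart, so the 24-hour rule is met and the same-day rule is not. Conversely, any two draws on one calendar day are within 24 hours. The same-day cases are thus a subset of the 24-hour cases, and the footnote can remove cases but never add one.

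**6. How often this could arise.** ALT, AST, bilirubin and alkaline phosphatase all belong to one chemistry panel (Protocol Table 6-2), and 9.5.1 says the analytes typically come from one sample. The repeat intervals in Section 9.5 (48 to 72 hours, then once or twice a week) are longer than 24 hours, so a split pair within 24 hours needs an extra draw. A remote Visit 12 has no laboratory draw, so tests after that visit would be unscheduled or follow-up tests.

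**The case against.** The best defence has three parts.

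**A reporting period need not equal an analysis period.** Section 9.5.1 governs what sites send to the sponsor; SAP 11.2 governs a table. A longer reporting period is not in itself an error. This stands. It does not excuse two ends for one duty inside 9.5.1, or an SAP window whose end has two meanings.

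**The intent of the 24-hour rule is obvious.** The row label, the row text, the SAP body and the protocol all say 24 hours, against one footnote. That is a fair guide to what was meant, but the footnote marker is still on the row and someone has to decide whether to program it.

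**Other outputs catch the case.** This is largely right. The e-DISH row takes maximum transaminase and bilirubin values at any time, so a split-sample case within the study appears there. Adjudicated elevations of ALT or AST of at least 3 × ULN are summarized and listed with no stated date limit or same-day rule. Participants with potentially clinically significant laboratory values have all their values displayed. None of these is the Hy's law count: e-DISH has no alkaline phosphatase condition, and the adjudication summary does not count Hy's law.

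A reader might infer that a case reported by a site and adjudicated could be missing from the SAP output altogether, or that the SAP closes its count on Day 308. The documents support neither. The adjudicated case is still summarized and listed, and Day 308 is only one reading of an undated phrase. Nor do the documents show that laboratory tests after Visit 12 will exist. They may, where an elevation is unresolved.

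**Conclusion.** The point holds as a matter of inconsistent rules, with a small expected effect. Protocol 9.5.1 gives one reporting duty two ends, 28 days apart for anyone who attends Visit 12 on schedule (22 to 34 days under the visit-window assumption above) and identical if that visit is not held. SAP 11.2 leaves it unclear whether a case on follow-up tests after Visit 12 is counted in the Hy's law row. Footnote 1 contradicts that row and works in one direction only.

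The possible loss is from the Hy's law count, or from site reporting if the shorter sentence is followed. It is not from all SAP output. The date problem matters only if a participant first meets the criteria after Visit 12; the footnote problem matters only if the qualifying values come from separate draws across midnight and no single panel qualifies. The documents give no basis for a probability of either, so I attach none. The contradictions should still be removed, because the event is a named special interest and the correction is nearly free.

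**What to change.** 1. **Protocol 9.5.1:** reconcile the two sentences to a single end date, including what applies when the final visit is not held. Which date is right is for the sponsor to decide.
2. **SAP 11.2:** replace the open reference to the end of study with an explicit counting window for potential Hy's law, matched to that date and stated to include unscheduled and follow-up liver tests. The start should be made explicit too: the protocol starts at consent and the SAP at first dose, without saying whether that is the lead-in or the open-label dose.
3. **SAP Table 18.1-1:** make the End of Study row agree with the note beneath the table.
4. **SAP Table 11-2:** remove footnote marker 1 from the potential Hy's law row so that the 24-hour rule alone applies. Keep it on the Concurrent Elevations row.

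The cost is one clarifying protocol sentence and a few lines of SAP text. No new visits or tests are needed, and at most a few more cases would be counted.
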